9.3.2. Treatment Group Comparability

9.3.2.1. Participant Disposition

A detailed description of participant disposition by treatment group will be provided, including the number of participants randomized to the study, treated in the study, discontinued from treatment with reason for discontinuation, and discontinued from the study with reason for discontinuation.

9.3.2.2. Participant Characteristics

A summary of baseline demographics and disease characteristics, historical diagnoses, preexisting conditions, and prior therapies will be reported by treatment group using descriptive statistics.

9.3.2.3. Concomitant Therapy

A summary of concomitant medications by treatment group will be provided.

9.3.2.4. Prior and Subsequent Anticancer Therapy

Prior and subsequent anticancer therapy used to treat CLL/SLL will be summarized by treatment group for applicable participants.

9.3.2.5. Extent of Exposure

The duration of therapy, dose modifications, and dose intensity for each treatment group will be summarized.

9.3.3. Primary Endpoints Analysis

The primary endpoint is ORR as assessed by investigator per iwCLL 2018 criteria (Section 8.1.4). ORR is defined as the proportion of participants who achieve the BOR of CR, CRi, nPR, or PR at or before the initiation of subsequent anticancer therapy.

The primary analysis will be conducted in the ITT population.

The ORR and the corresponding CCI will be summarized for each treatment group.

CCI will be used to test for differences in ORR. CCI on the point estimates of the differences in ORR will be summarized.

Further details will be provided in the SAP.

9.3.4. Secondary Endpoints Analysis

Duration of response

Investigator-assessed DOR is defined as the time from first documented response of CR, CRi, nPR, or PR to the first documentation of disease progression (per iwCLL 2018 criteria, Section 8.1.3) or death from any cause. Following first documentation of CR, CRi, nPR, or PR, participants who are alive and without documented disease progression at the time of the data analysis cutoff date will be censored. A detailed DOR event/censoring scheme will be provided in the SAP.

Median DOR and its CCI and DOR rates and associated CCI at selected timepoints, for each treatment group will be estimated CCI CCI

Safety analysis

Safety data will be summarized for the safety population. The baseline value for the safety analysis is defined as the value collected at the time closest to and before the start of study intervention administration.

AEs will be graded by the investigator according to the NCI CTCAE v5.0 for nonhematologic and hematologic AEs. Each AE verbatim term will be coded to a System Organ Class and a Preferred Term using the MedDRA.

All TEAEs will be summarized by treatment group, including severity and relationship to study intervention.

Summaries by treatment group will be provided for the following, but not limited to

- ≥Grade 3 AESIs
- ≥Grade 3 TEAEs
- SAEs
- discontinuations due to an AE
- dose interruptions due to an AE, and
- dose reductions due to an AE.

Estimates of key safety measures will be summarized with CCI for each treatment group.

Clinical laboratory parameters will be summarized by treatment and the worst postbaseline toxicity grade that occurs during the treatment period.

Serum immunoglobulins (IgA, IgG, and IgM) will be summarized with descriptive statistics. Participants who receive IV immunoglobulin during the study will be excluded from the summary for IgG.

Additional safety endpoints, including ECOG PS, vital signs, and weight, will be summarized descriptively with further details provided in the SAP.

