HCV	X						If HCV antibody test is positive, it must be followed by an HCV RNA test. See Section 5.2.
HBV	X	X					See Sections 5.2 and 8.2.7 for details.
CMV PCR	X						
Immunoglobulin panel	X						
Coagulation panel	X	X					After screening: As clinically indicated.

Study JZNX	Screening	Study Treatment Cycle = 28 days			Posttreatment		Instructions
Cycle/Visit	Baseline (Day Relative to C1D1)	Cycles 1-6	Cycles 7-24	Cycles 25+	Short- Term Follow-Up (STFU)	Long- Term Follow- Up ^{††} (LTFU)	Cycles 1-6: visits occur at each cycle. Cycles 7-24: visits occur Q16W at C9, C13, C17, C21, and C25. Cycles 25+: visits occur Q24W. ^{††} Occurs every 16 weeks for first 2 years relative to C1D1, and then every 24 weeks.
Day of cycle or visit		Day 1	Day 1	Day 1	V801	V802-8XX	
Visit window (days)	Up to 28	± 7	± 14	± 14	28 + 7	±14	C1D1: see visit window instructions in Section 1.3.
Pregnancy test (serum or urine)	X	X			X		Collect for individuals of childbearing potential. See Section 10.4 for definitions. Screening: Serum sample preferred. C1D1: Perform within 24 hr before the first dose of pirtobrutinib. At any time during the study: monthly or as required per local regulations or institutional guidelines. STFU: Serum sample preferred.
Bone marrow biopsy		X					Only collect and evaluate locally to confirm CR or disease progression due to cytopenia. See Section 8.1.3.
CCI							
Stored samples							
CCI							
Randomization, dosing, dosing diary, and IWRS							
Register visit with IWRS	X	X	X	X	X		Visits are C1-6, C9, C13, C17, C21, C25, and then Q24W.
Randomization via IWRS	X						Upon confirmation of eligibility.
Dispense pirtobrutinib		X	X	X			Dosing is oral daily (continuous).
Dispense participant dosing diary		X					

Study JZNX	Screening	Study Treatment Cycle = 28 days			Posttreatment		Instructions
Cycle/Visit	Baseline (Day Relative to C1D1)	Cycles 1-6	Cycles 7-24	Cycles 25+	Short- Term Follow-Up (STFU)	Long- Term Follow- Up ^{††} (LTFU)	Cycles 1-6: visits occur at each cycle. Cycles 7-24: visits occur Q16W at C9, C13, C17, C21, and C25. Cycles 25+: visits occur Q24W. ^{††} Occurs every 16 weeks for first 2 years relative to C1D1, and then every 24 weeks.
Day of cycle or visit		Day 1	Day 1	Day 1	V801	V802-8XX	
Visit window (days)	Up to 28	± 7	± 14	± 14	28 + 7	±14	C1D1: see visit window instructions in Section 1.3.
Participant returns dosing diary for site review		X					
Assess dosing compliance		X	X	X			
Participant status							
Survival status		X					

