6.9.3. Concomitant Therapy for Infections or Bleeding

See Section 8.2.7 for more information on monitoring for infections and bleeding.

Infections

The use of prophylactic antimicrobial therapy should be considered in all study participants when clinically appropriate. Local practices or guidelines regarding infection prophylaxis should be followed.

Prophylactic antibiotic or IV immunoglobulin therapy for management of participants at risk of infections may be considered. Initiation of prophylactic antibiotics against pneumocystis infection before study intervention administration may be warranted.

Examples of antimicrobial therapy include

- trimethoprim-sulfamethoxazole
- dapsone
- aerosolized pentamidine, and
- atovaquone.

Bleeding

The benefit versus risk of concurrent treatment with anticoagulation and antiplatelet therapy should be carefully considered for participants who require this therapy.

If a participant needs surgery, the benefit versus risk of withholding anticoagulation or antiplatelet therapy for at least 3 to days before and after surgery should be considered depending upon the type of surgery and the risk of bleeding.

The sponsor recommends withholding pirtobrutinib for at least 3 days before and after surgery where bleeding risk cannot be excluded.

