8.3.3. Adverse Events of Special Interest

Adverse events of special interest for this study include

- hemorrhage
- cytopenia
- infections, and
- atrial fibrillation/atrial flutter.

More detailed information on these AEs may be found in the IB and prescribing information.

The investigator may consider modifying the dose of pirtobrutinib, for participants experiencing AESI events described in Section 6.6.

Hemorrhage***Causes of hemorrhage in this study population***

Bleeding, mainly low-grade, nonserious events of bruising and bleeding, is a recognized drug class effect of BTK inhibitor therapy.

Participant monitoring for bleeding

This study includes routine monitoring of blood count, for cases of bleeding for all participants (Section 1.3).

If a participant shows signs of bruising or bleeding, the investigator should consider checking a coagulation laboratory panel.

Cytopenia

Cytopenia is a low level of certain blood cells, such as neutropenia, anemia, or thrombocytopenia.

Causes of cytopenia in this study population

Causes of cytopenia include complications from the disease or complications from a participant's therapy. Cytopenia is a recognized drug class effect of BTK inhibitor therapy.

Individuals receiving pirtobrutinib mainly experienced neutropenia followed by anemia and thrombocytopenia.

Participant monitoring for cytopenia

This study includes routine hematologic monitoring throughout the study for all participants (Section 1.3).

If a participant develops neutropenia, the investigator should monitor the participant for increased risk of infection, as clinically appropriate.

If a participant develops thrombocytopenia, the investigator should monitor the participant for increased risk of bleeding, as clinically appropriate.

Infections

Causes of infection in this study population

Increased occurrence or severity of infections risk is a recognized risk of BTK inhibitor therapy. The risks include life-threatening, opportunistic, and fatal infections, including sepsis, and sepsis shock. These risks may increase due to a participant's underlying disease, age, prior treatment history, or comorbidities.

Participant monitoring for infections

The investigator will monitor participants throughout the study for signs of infection, particularly those with additional risk factors, such as participants that have poor bone marrow function, ongoing neutropenia, or diabetes.

Atrial fibrillation/flutter

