10.2. Appendix 2: Clinical Laboratory Tests

The tests detailed in the table below will be performed by the local laboratory or a Lilly-designated laboratory.

In circumstances where the sponsor approves local laboratory testing in lieu of central laboratory testing, the local laboratory must be qualified in accordance with applicable local regulations.

Additional tests may be performed at any time during the study as determined necessary by the investigator or required by local regulations.

Investigators must document their review of the laboratory safety results.

Clinical Laboratory Tests	Comments
Hematology	Locally performed
Hemoglobin	
Hematocrit	
Erythrocyte count (RBCs - red blood cells)	
Leukocytes (WBCs - white blood cells)	
Differential	
Percent and/or absolute count of:	
Neutrophils	Neutrophils reported by automated differential hematology instruments may include both segmented and band forms. When a manual differential is needed to report the neutrophils, the segmented and band forms should be added together and recorded on the CRF
Lymphocytes	
Monocytes	
Eosinophils	
Basophils	
Platelets	
Coagulation	Locally performed
International normalized ratio (INR) or prothrombin time (PT)	
Activated partial thromboplastin time (aPTT) or PTT	
Clinical chemistry	Locally performed
Sodium	
Potassium	
Chloride	
Blood urea nitrogen (BUN) or blood urea	
Creatinine	
Creatine kinase (CK)	
Alkaline phosphatase (ALP)	
Alanine aminotransferase (ALT)	
Aspartate aminotransferase (AST)	
Total bilirubin	

Clinical Laboratory Tests	Comments
Direct bilirubin	
Total protein	
Albumin	
Calcium (serum)	
Magnesium	
Phosphorus	
Uric acid	
Lactate dehydrogenase (LDH)	
Glucose (random)	
Urinalysis	Locally performed
Specific gravity	
pH	
Protein	
Glucose	
Ketones	
Bilirubin	
Urobilinogen	
Blood	
Nitrite	
Urine leukocyte esterase	Urine microscopy may be used in the place of the urine leukocyte esterase assessment to test for the presence of WBCs
Microscopic examination of sediment	If clinically indicated
Pregnancy test	Locally performed
Serum pregnancy	For participants of childbearing potential
Urine pregnancy	For participants of childbearing potential
Hepatitis serology and CMV	Locally performed
Hepatitis B Virus (HBV) testing	All participants should have serology, including hepatitis B surface antigen and hepatitis B core total antibody or an HBV DNA
HBV DNA	Collect only if necessary to determine eligibility as per Section 5.2
Hepatitis C Virus (HCV) testing	
CMV PCR	

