Pharmacokinetic samples pirtobrutinib concentration	Assayed by Lilly-designated laboratory. Results will not be provided to the investigative sites
Immunoglobulin panel	Locally performed
IgA	
IgE	
IgG	
IgM	

10.3. Appendix 3: Adverse Events and Serious Adverse Events: Definitions and Procedures for Recording, Evaluating, Follow-Up, and Reporting

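### The IgG summary drops whole participants given IV immunoglobulin on study, although the only scheduled IgG sample is taken at screening

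*Supplement*

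**What the plan says.** The safety part of protocol Section 9.3.4 bases its summaries on the safety population. On immunoglobulins it says: "Serum immunoglobulins (IgA, IgG, and IgM) will be summarized with descriptive statistics". It names no time points and no change from baseline. The next sentence sets the exclusion: "Participants who receive IV immunoglobulin during the study will be excluded from the summary for IgG". It applies to IgG alone, it excludes participants rather than values, and it has no time qualifier. The same section fixes the baseline: "The baseline value for the safety analysis is defined as the value collected at the time closest to and before the start of study intervention".

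In Section 1.3.1 the row "Immunoglobulin panel" carries a single mark, under Screening, and its instruction cell is empty. Section 10.2 lists IgA, IgE, IgG and IgM as "Locally performed", without timing.

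On use of the product, Section 6.9.3 says: "Prophylactic antibiotic or IV immunoglobulin therapy for management of participants at risk of infections may be considered". It gives no IgG threshold. Infections are an adverse event of special interest in Section 8.3.3.

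**The concern.** Leaving out IgG measured after an infusion is sensible, because infused IgG raises the measured level. The rule goes further. One infusion late in treatment removes all of that participant's IgG values, including those taken before it.

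Two things follow. First, membership of the IgG table depends on a discretionary treatment decision made after randomization in an open-label comparison of doses. If that decision is taken more often for participants with low IgG, the remaining mean is too high. If it is taken more often in one arm, the remaining groups are no longer the randomized ones. Even the screening values could then show a difference between arms that later treatment created.

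Second, the analysis text and the schedule do not fit together. The exclusion has a purpose only for samples taken after an infusion, and the schedule plans no sample after screening.

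**Working it through.** **1. Which IgG values will exist.**
- Scheduled: one, at screening (Section 1.3.1). Neighbouring rows such as HBV and the coagulation panel keep a second mark under Cycles 1-6, so the single mark is unlikely to be a fault of text extraction.
- Event-driven: IgA, IgG and IgM in the liver work-up list (Section 10.5).
- Discretionary: "Additional tests may be performed at any time during the study as determined necessary by the investigator or required by local regulations" (Section 10.2).

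The last two are not a planned series. Under the safety baseline definition, the IgG baseline is in practice the screening value.

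**2. What the rule does to them.** An infusion given after the screening sample cannot affect that sample, yet the participant's value is removed. IgA and IgM keep everyone, so the three summaries rest on different participants.

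**3. Size (illustration only).** The plan gives no figure to reproduce. Let q be the share of an arm excluded and ρ the correlation between low IgG and receipt of immunoglobulin. Both are assumptions. With a normal latent tendency to receive it, and with φ the standard normal density and z_q its q-quantile, the upward shift in mean IgG, in SD units, is

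shift = ρ · φ(z_q) / (1 − q).

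For q = 0.10, φ(z_q) = 0.1755. Then 0.1755 / 0.90 = 0.195, which is multiplied by ρ.

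| q | ρ = 0 | ρ = 0.3 | ρ = 0.5 | ρ = 1 (sharp cut-off) |
|---|---|---|---|---|
| 5% | 0 | 0.033 | 0.054 | 0.109 |
| 10% | 0 | 0.058 | 0.097 | 0.195 |
| 15% | 0 | 0.082 | 0.137 | 0.274 |
| 20% | 0 | 0.105 | 0.175 | 0.350 |
| 30% | 0 | 0.149 | 0.248 | 0.497 |

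**4. Difference between arms.** With 5% use in one arm and 15% in another, the false difference is the gap between those two rows: about 0.05 SD at ρ = 0.3, 0.08 at ρ = 0.5 and 0.17 at ρ = 1. With equal use and equal ρ it is zero.

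**5. Numbers left.** Section 9.5 plans about 249 participants. The allocation ratio is redacted. If it is equal, 249 / 3 = 83 per arm, and 83 × (1 − q) leaves 79, 75, 71, 66 or 58 at the five values of q.

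**6. After the change.** If only values after the first on-study dose are set aside, a screening sample taken before it is always kept. The selection shift in the baseline summary is then zero.

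**The case against.** **The table is descriptive and other summaries cover the safety question.** This stands. Infections of Grade 3 or higher are summarized among the events of special interest, all treatment-emergent events are summarized by arm, and IgA and IgM keep everyone. The concomitant-medication summary (Section 9.3.2.3) should already show immunoglobulin use by arm. No test or dose decision is said to rest on the IgG table.

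**The SAP may apply the exclusion by date.** It may. Section 9 describes itself as a summary, and Section 9.3.1 leaves the handling of missing and unused data to the SAP, which was not available for this review. But the protocol states this rule without qualification and without deferring its details, so a value-level rule in the SAP would still need the protocol sentence changed.

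**Three stronger readings are tempting and should not be drawn.**
- A reader might infer that the participants with the lowest IgG are exactly those removed. Section 6.9.3 refers only to risk of infection, and Sections 8.2.8 and 8.3.3 list other risk factors, such as neutropenia, poor marrow function and diabetes. A link with low IgG is likely, but it is an inference.
- A reader might infer that the rule hides a dose effect on IgG. With screening samples only, the table can neither show nor hide one.
- A reader might take the sharp cut-off column as the expected size. It is the worst case, because it assumes that everyone below some IgG level, and nobody above it, receives immunoglobulin.

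**Conclusion.** The point holds as a minor one. As worded, the rule removes pre-treatment IgG values because of a later event that could not have affected them, and it makes the IgG population differ from that for IgA and IgM. The consequence is a selected baseline description. Summaries by arm would also be biased if unscheduled on-treatment values, or samples added later, enter the table.

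The direction is upward if recipients tend to have lower IgG. The size is unknown. The range of about 0.03-0.25 SD rests on assumed use of 5-30% and an assumed correlation of 0.3-0.5, and at zero correlation there is no shift. The primary endpoint and the planned comparisons of adverse events are not touched.

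**What to change.** Replace the exclusion sentence in Section 9.3.4 with wording such as: all participants in the safety population contribute IgG values up to their first on-study IV immunoglobulin dose; values after that dose are set aside; the number of recipients is shown by treatment group.

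Then reconcile the section with the Schedule of Activities. If screening is the only intended sample, label the immunoglobulin table as baseline. If an on-treatment summary is intended, state which post-baseline samples it uses and show them in the schedule. Carry the same rule into the SAP.

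The cost is one sentence, a date filter in the programming and a table label. It is larger only if post-baseline sampling was intended and has to be added. Nothing here alters when immunoglobulin may be given.

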9.3.5. Pharmacokinetic and Pharmacodynamic Analyses

Pirtobrutinib plasma concentrations will be summarized by descriptive statistics. Additional analysis utilizing the population PK approach may also be conducted if deemed appropriate.

The relationship between pirtobrutinib plasma exposure and selected efficacy and safety outcomes may be explored.

9.3.6. Other Analyses

9.3.6.1. Other Efficacy Analysis

Progression-free survival

Investigator-assessed PFS is defined as the time from randomization until documented disease progression (per iwCLL 2018 criteria) or death from any cause, whichever occurs first. Participants known to be alive and without documented disease progression at the time of the data analysis cutoff date will be censored at the date of the last adequate disease assessment. A detailed PFS event or censoring scheme will be provided in the SAP.

Median PFS and its CCI and PFS rates and associated CCI at selected timepoints, for each treatment group will be estimated using the CCI

Overall survival

OS is defined as the time from randomization until death from any cause. If the participant is alive or lost to follow-up at the time of the data analysis cutoff date, OS data will be censored on the last date the participant is known to be alive. A detailed OS event or censoring scheme will be provided in the SAP. Median OS and its CCI and OS rates and associated CCI at selected timepoints, for each treatment group will be estimated using CCI

9.3.6.2. Biomarker Analysis

Biomarker results will be summarized and may be analyzed for correlation with clinical outcomes (both efficacy and safety), if feasible.

9.3.6.3. Subgroup Analyses

Subgroup analyses will be performed if deemed necessary. The details will be in the SAP.

9.4. Interim Analysis

No interim analyses are planned for this study. If an unplanned interim analysis is deemed necessary for reasons other than a safety concern, the protocol must be amended.

An AC internal to Lilly will conduct a periodic safety and efficacy data review during the study (Section 10.1.5).

9.5. Sample Size Determination

Approximately 249 participants will be randomly assigned in a CCI ratio to receive either pirtobrutinib 200 mg, CCI approximately CCI participants per dose level.

The superiority of pirtobrutinib 200 mg versus CCI as measured by investigator-assessed ORR will be tested using a CCI. With CCI participants per dose level, there is CCI power to detect a difference in ORR, assuming a CCI ORR with pirtobrutinib 200 mg and CCI ORR CCI. Efficacy boundary on the difference in ORR is approximately CCI.

CCI

The CCI ORR assumed for pirtobrutinib 200 mg is based on the results from Study 18001 for participants with CLL/SLL who were previously treated with BTK inhibitors and received pirtobrutinib at a starting dose of 200 mg. Given limited efficacy data from Study 18001 at lower dose levels, a CCI ORR was assumed for CCI since a CCI shift in true ORR (efficacy boundary of CCI is the minimal clinically meaningful difference in which the efficacy at lower doses is clearly worse than the efficacy of pirtobrutinib 200 mg.

Additionally, a sample size of CCI participants per dose level will provide approximately CCI power to detect a difference in the occurrence of Grade 3 or higher treatment-emergent AEs between any two dose levels, when the assumed incidence rates are CCI. These comparisons on treatment-emergent AEs will not be CCI CCI

10. Supporting Documentation and Operational Considerations

